8.1 Sample Size Considerations

The number of Participants to be enrolled in this 6-month extension study depends upon the number of subjects who complete the Day 180 Visit in Study VMDN-003-2 and provide written informed consent for this extension protocol (prior to or during their Day 180 Visit in the VMDN-003-2 study).

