10.6.1 Missing Pain Scores for the Average Scores from BPI-DPN

The means of the Average Daily Pain Scores (Question 5 from the BPI-DPN) for a visit will be considered as missing if fewer than 5 of 7 days of BPI-DPN eDiary entries are provided. Any missing mean pain score of ADPS will be imputed using the methods described below.

Multiple Imputation (MI) method:

- Step 1: Intermittent missing values will first be imputed by treatment group using the Markov Chain Monte Carlo (MCMC) method, resulting in data with a monotone pattern.
- Step 2: Multiple imputation by treatment group using linear mixed model regression with factors of baseline pain score, baseline HbA1c, gender, and age at informed consent (Study VMDN-003-2) will be applied to the data obtained from the MCMC step. The imputed score will be rounded to the first decimal point.

The entire procedure will be repeated 10 times, and 10 complete datasets will be used for the analysis.

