12.0 Statistical Methods

The primary analysis for this study will be performed and summarized after all randomized participants have had an opportunity to complete their 12-month follow-up visit.

The Safety Analysis will be based on the Safety population. The primary analyses of the efficacy endpoints will be based on the ITT population. Additional sensitivity analyses for the primary and secondary efficacy endpoints will be performed to further assess the effects of the treatment (Section 8.4.2 and 8.4.4).

The statistical analyses will be reported using summary tables, figures and listings. Continuous variables will be summarized with mean, standard deviation, median, minimum, maximum, 25th percentile, 75th percentile, and number of non-missing observations for each treatment group.

Categorical variables will be summarized by counts and by the percentage of participants in corresponding categories.

All inferential statistical analyses will be performed with a two-sided confidence level of 95% or a two-sided significance level of 0.05 unless otherwise noted.

All analyses and tabulations will be performed using SAS Version 9.4 or higher on a Server platform.

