12.5 Efficacy Analyses

12.5.1 Primary Analysis of the Primary Efficacy Endpoint

The primary analysis for comparing the change in mean Average Daily Pain Scores at the Day 365 visit from Baseline between the treatment groups will be analyzed using the MI method for handling the missing data as specified in Section 10.6.1. A linear mixed-effects model for repeated measures (hereinafter, the continuous Repeated Measures Model) will be used to analyze each complete dataset. The model will include treatment, visit (Day 90 and Day 180 from main study, Day 270 and 365 from extension study), treatment-by-visit interaction, and baseline (Study VMDN-003-2) Average Daily Pain Score as a covariate using an unstructured variance-covariance matrix. Then the Proc MIANALYZE procedures will be used to generate the point estimate for the least-squares mean of the treatment difference (Engensis – Placebo)

and the corresponding 95% confidence interval. LSMEANS, differences and p values compared to baseline will be presented for Day 90 and Day 180 visits from the main study, and Day 270 and Day 365 at the extension study.

The SAS code to be used to for the continuous repeated measure model is presented below:

```
proc mixed data=work order=internal method = REML;
class usubjid trtp avisitn;
model chg = trtp avisitn trtp*avisitn base / ddfm=KR;
repeated avisitn /subject = usubjid type = un;
lsmeans trtp trtp*avisitn / pdiff cl;
run;
```

where

USUBJID: subject ID TRTP: treatment

AVISITN: variable representing visits

CHG: change in the Average Daily Pain Score from baseline(Study VMDN-003-2)

BASE: baseline (Study VMDN-003-2) Average Daily Pain Score (continuous variable)

Other variance-covariance structures selected from among compound symmetry, Toeplitz, and autoregressive (1) options will be substituted based on the lowest Akaike information criterion (AIC) if convergence problems arise.

The primary efficacy analysis will be performed for ITT population.

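### With 10 imputations a borderline primary or responder result can change its significance call between runs; the test stays valid, and a larger number costs almost nothing.

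*SAP*

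**What the plan says.** SAP section 10.6.1 treats a visit's mean Average Daily Pain Score (ADPS) as missing when diary entries are too few: it "will be considered as missing if fewer than 5 of 7 days of BPI-DPN eDiary entries are provided". Gaps are filled in two random steps. First, "Intermittent missing values will first be imputed by treatment group using the Markov Chain Monte Carlo (MCMC) method". A regression imputation by arm then completes the monotone pattern. On the number of imputations: "The entire procedure will be repeated 10 times, and 10 complete datasets will be used for the analysis".

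SAP section 12.5.1 makes the primary comparison depend on these datasets, because the Day 365 change in mean ADPS "will be analyzed using the MI method for handling the missing data as specified in Section 10.6.1". The repeated measures model is fitted to each completed dataset and the results are pooled: "Then the Proc MIANALYZE procedures will be used to generate the point estimate for the least-squares mean of the treatment difference". SAP section 12.0 sets "a two-sided significance level of 0.05 unless otherwise noted". SAP section 12.5.2.2 uses the same 10 datasets for the 50% responder endpoint.

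The SAP text supplied states no random seed, no reason for choosing 10, no check of Monte Carlo error and no rule for raising the number.

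**The concern.** Each imputation run draws new random values, so the pooled estimate, its standard error and its p-value vary from run to run even though the trial data do not. The usual argument for a small number of imputations is that the point estimate loses little efficiency. That is true here, but it does not show how far the p-value can move.

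If the primary result is close to 0.05, two analysts who both follow the SAP exactly could report different significance calls. The responder test carries the same risk. Without a stated seed, a reader of the SAP also cannot tell which run was the planned one.

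**Working it through.** **Inputs from the documents.** Number of imputations m = 10 (SAP 10.6.1). Pooling by PROC MIANALYZE, that is, Rubin's rules (SAP 12.5.1). Two-sided alpha 0.05 (SAP 12.0). The documents contain no derivation of m = 10 to reproduce.

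**Inputs assumed.** SAP section 10.6 expects withdrawals and missed visits, but neither document gives a missing-data rate or a sample size (SAP 8.1: "The number of Participants to be enrolled in this 6-month extension study depends upon the number of subjects who complete the Day 180 Visit"). FMI is therefore taken as 5%, 10%, 20% and 30%. For a given FMI, the calculation below does not need the sample size.

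**Step 1. Efficiency of the point estimate.** Relative efficiency is 1/(1 + FMI/m). At m = 10 it is 1/(1 + 0.05/10) = 0.995 at FMI 5%, 1/(1 + 0.2/10) = 0.980 at FMI 20% and 1/(1 + 0.3/10) = 0.971 at FMI 30%. The loss is small.

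**Step 2. Monte Carlo error, by hand.** In units of the standard error, the run-to-run SD of the pooled estimate is about sqrt(FMI/m). At FMI 20%:

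- m = 10: sqrt(0.2/10) = 0.141. A limiting z of 1.96 ranges over 1.96 ± 1.96 × 0.141, or 1.68 to 2.24, so p runs from 0.025 to 0.092.
- m = 100: sqrt(0.2/100) = 0.045. The range is 1.96 ± 1.96 × 0.045, or 1.87 to 2.05, so p runs from 0.041 to 0.061.

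This approximation leaves out two parts of the planned pooling: noise in the between-imputation variance and the t reference distribution. Both widen the range.

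**Step 3. Full Rubin's rules, by simulation.** Hold the trial data fixed and scale the total variance to 1. Draw the pooled estimate from N(z, FMI/m) and the between-imputation variance B from FMI × chi-square(m − 1)/(m − 1). With within-imputation variance U = 1 − FMI, set T = U + (1 + 1/m)B and r = (1 + 1/m)B/U. Refer estimate/sqrt(T) to t with (m − 1)(1 + 1/r)² degrees of freedom.

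Central 95% of p-values over runs, when the large-m p is 0.05:

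| FMI | m = 10 | m = 100 |
|---|---|---|
| 5% | 0.036-0.071 | 0.045-0.056 |
| 10% | 0.030-0.084 | 0.043-0.059 |
| 20% | 0.023-0.109 | 0.039-0.064 |
| 30% | 0.018-0.134 | 0.036-0.068 |

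Share of runs giving p of 0.05 or more, when the large-m p is 0.04:

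| FMI | m = 10 | m = 100 |
|---|---|---|
| 5% | 12% | 0% |
| 10% | 23% | 0.4% |
| 20% | 35% | 4% |
| 30% | 41% | 10% |

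At m = 200 this share is 3% or less throughout. If the large-m p is 0.03, the share at m = 10 is 0.4%, 4%, 16% and 25% in the same FMI order.

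**Step 4. How often it matters overall.** Let the trial data vary too, and compare two independent m = 10 runs on the same data. Over FMI 5-20% they disagree on significance in about 1-2% of trials under no effect, 2-6% at an assumed 80% power and 1.5-3.7% at an assumed 90% power. At m = 100 and FMI 20% the figure is 0.7-1.7% across these cases. Type I error at m = 10 is about 0.05, and the power loss at FMI 20% is about 1 percentage point.

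**Step 5. Check on simulated trials.** Two-arm datasets with a large-m p near 0.05 were each re-imputed with 300 seeds at m = 10. Assumptions were 50 or 75 per arm, visit correlation 0.5 or 0.7, and 5-30% missing at Day 365. The widest limits of the central 95% were about 0.032-0.076 with 5% missing, 0.026-0.095 with 10%, 0.020-0.110 with 20% and 0.018-0.153 with 30%. Both significance calls occurred in all 16 scenarios. This check used analysis of covariance at Day 365 and monotone missingness, not the full planned model.

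**The case against.** The best defence is that 10 imputations is a valid choice. Rubin's variance includes the (1 + 1/m) term, so finite m is already paid for, and the calculation bears this out. A reader might infer from the p-value ranges that the primary test is biased or that its type I error is inflated. The documents do not support that: the issue is reproducibility near the threshold.

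Second, the size rests on an FMI that the documents do not give, and several features limit missingness. The ITT set contains only participants who start the extension at Day 180 (SAP 9.1). A visit with too few diary entries must be rescheduled (protocol 8.2.1). Diary data count even if the visit is missed (SAP 10.3). This is fair. None of it shows that missingness will be negligible, but it is why the range starts at 5%, where the effect is modest.

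Third, the large percentages presuppose a borderline result. They should not be read as the chance that this trial's conclusion will flip; step 4 gives that figure, and it is low.

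Fourth, a reader might infer that no seed exists or that runs could be chosen after the fact. The SAP text supplied does not show this. A seed may sit in programming specifications, which were not supplied, and parts of the SAP are redacted.

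The planned sensitivity analyses do not answer the point. The mITT and PP sets require an adequate Day 365 diary (SAP 9.3 and 9.4), so Day 365 is not imputed there. The prohibited-medication analysis (SAP 12.5.1.1) is not designed to show variation between imputation runs.

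**Conclusion.** The point holds as one of precision and reproducibility. At every assumed FMI from 5% to 30%, a primary result near 0.05 can change its significance call with the imputation run at m = 10. The responder result is exposed in the same way at a given FMI; its own FMI is likewise unknown. A clearly positive or clearly null result would not be affected. At FMI 5% even a large-m p of 0.03 crosses 0.05 in only 0.4% of runs.

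The analysis as planned is valid, so this is a worthwhile, nearly free improvement to the SAP and not the correction of an error. The figures depend on the assumed FMI and should be revisited if a blinded estimate of missing Day 365 data becomes available.

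**What to change.** In SAP section 10.6.1, replace 10 with at least 100 imputations, or 200 if FMI may reach 20% or more. State a fixed random seed in the same section. Make both changes before the randomization codes are unmasked after database lock (SAP 10.4).

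The two changes do different jobs. The larger number reduces the noise. The seed only makes the run repeatable and rules out choosing among runs. If a seed already exists in the programming specifications, the SAP need only cite it.

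The imputation model, analysis model, population and endpoint definitions stay as they are. The cost is a short edit and a little computing time.

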10.6.2 Addressing Missing Data for the Secondary and Exploratory Efficacy

Missing individual item scores of the full BPI-DPN will be imputed for the calculation of the average score within a domain using the average score across the non-missing items within the domain at a subject's visit provided that the proportion of missing items scores within that domain is less than 25%; otherwise, the domain score at that visit is missing.

The same method as the full BPI-DPN will be used when addressing the missing data for SF-36 and EQ-5D.

Individual item scores on the MNSI (both physical assessment and history) questionnaire will not be imputed. The total MNSI scores will be imputed using a "worst-case" imputation approach. Missing individual items will be imputed as the category corresponding to the largest number of points in the total score calculation. This equates to a response of "Yes" to questions 1-3, 5-6, 8-9, 11-12, and 14-15 and "No" to questions 7 and 13 on the history assessment. On the physical assessment, it equates to a response of "No" on the "Appearance of Feet" question, a response of "Present" on the "Ulceration" question, and a response of "Absent" on the "Ankle Reflexes", "Vibration perception at great toe", and "Monofilament" questions.

Missing PGIC and BST scores and the use of rescue medication will not be imputed.

10.6.3 Missing Dates

If a start or stop date for an adverse event or a concomitant medication use is completely missing, it will not be imputed. If it is partially missing, imputed dates in accordance with Table 1 will be used to derive the duration of the adverse event or the duration of the medication use. Missing years will not be estimated under any conditions. Missing dates of medical history will not be imputed.

Table 1: Imputation Rules for Partial Adverse Event or Concomitant Medication Start and Stop Dates

	Missing	Imputation	Exception
Start Date	Day	01	Default to Study Day 180 +1 (first date in extension study) if an event starts in the same year and month as Study Day 180

	Day/Month	01JAN	Default to Study Day 180 + 1 if an event starts in the same year as Day 180
Start Date			If the start date is completely missing and stop date is either after the date of Study Day 180 + 1 or completely missing, then the start date will be estimated to be equal to Study Day 180 + 1. Otherwise, the start date will be estimated to be the first day of the same year as the stop date.
Stop Date	Day	Last day of the month	Default to the End of Study Date if the imputed event stop date is after the End of Study Date or before start day of the event
	Day/Month	31DEC	

11.0 Interim Analyses

There will be no interim analysis during this 6-month extension study.

12.0 Statistical Methods

The primary analysis for this study will be performed and summarized after all randomized participants have had an opportunity to complete their 12-month follow-up visit.

The Safety Analysis will be based on the Safety population. The primary analyses of the efficacy endpoints will be based on the ITT population. Additional sensitivity analyses for the primary and secondary efficacy endpoints will be performed to further assess the effects of the treatment (Section 8.4.2 and 8.4.4).

The statistical analyses will be reported using summary tables, figures and listings. Continuous variables will be summarized with mean, standard deviation, median, minimum, maximum, 25th percentile, 75th percentile, and number of non-missing observations for each treatment group.

Categorical variables will be summarized by counts and by the percentage of participants in corresponding categories.

All inferential statistical analyses will be performed with a two-sided confidence level of 95% or a two-sided significance level of 0.05 unless otherwise noted.

All analyses and tabulations will be performed using SAS Version 9.4 or higher on a Server platform.

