9.3.2. Secondary Endpoints

The secondary efficacy endpoints include the following:

- Change in the means of the Worst Pain scores from the full BPI-DPN from the 7 days prior to the Day 0 Visit (Study VMDN 003 2) to the 7 days prior to the Day 270 Visit and the 7 days prior to the Day 365 Visit for Engensis compared to Placebo
- Proportion of Responders (≥ 50% reduction in the ADPSs from the full BPI-DPN) from the 7 days prior to the Day 0 Visit (Study VMDN-003-2) to the 7 days prior to the Day 270 Visit and the 7 days prior to the Day 365 Visit for Engensis compared to Placebo

Secondary safety endpoints include:

- Incidence of TEAEs and TESAEs for Engensis compared to Placebo
- Incidence of clinically significant laboratory values for Engensis compared to Placebo

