7.0 Study Objectives

Objectives	Endpoints
Primary	

 To evaluate the efficacy of IM administration of Engensis on pain in participants with painful DPN in the feet and lower legs, as compared to Placebo 	
 Change in the means of the Average Daily Pain Scores (ADPSs) from the Brief Pain Inventory for Diabetic Peripheral Neuropathy (BPI-DPN) from the 7 days prior to the Day 0 Visit (Study VMDN-003-2) to the 7 days prior to the Day 365 Visit for Engensis compared to Placebo in the intent-to-treat (ITT) population
Secondary Efficacy	

 To evaluate the efficacy of IM administration of Engensis on the worst pain in Participants with painful DPN in the feet and lower legs as compared to Placebo 	
 Change in the means of the Worst Pain Scores from the BPI-DPN from the 7 days prior to the Day 0 Visit (Study VMDN-003-2) to the 7 days prior to the Day 270 Visit and Day 365 Visit for Engensis compared to Placebo

 To evaluate the efficacy of IM administration of Engensis on reducing pain in Participants with painful DPN in the feet and lower legs as compared to Placebo 	
 Proportion of Responders ($\geq 50\%$ reduction in the means of ADPSs from the BPI-DPN) from the 7 days prior to the Day 0 Visit (Study VMDN-003-2) to the 7 days prior to the Day 270 Visit and Day 365 Visit for Engensis compared to Placebo

Objectives	Endpoints
Secondary Safety	

 To evaluate the safety of IM administration of Engensis in Participants with painful DPN in the feet and lower legs as compared to Placebo 	
 Incidence of treatment-emergent adverse events (TEAEs) and treatment-emergent serious adverse events (TESAEs) for Engensis compared to Placebo Incidence of clinically significant laboratory values for Engensis compared to Placebo
[REDACTED]	

 [REDACTED] 	
 [REDACTED]

 [REDACTED] 	
 [REDACTED]

 [REDACTED] 	
 [REDACTED] [REDACTED]

Objectives	Endpoints
	
 █ [REDACTED] █ [REDACTED] █ [REDACTED] █ [REDACTED] █ [REDACTED]

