10.5 Data Safety Monitoring Board

An independent DSMB will periodically review a limited set of unblinded tables and/or listings, including all reported AEs. The objectives of the DSMB meetings are to review the safety outcomes of the study and provide guidance to the study sponsor regarding the safety of the Engensis. The data analyses for the DSMB meetings will be directly provided to the DSMB members and no data will be released to the study sponsor and blinded designees. There will be no adjustment for multiple testing due to the DSMB data review. The DSMB may be asked to review and provide guidance regarding protocol deviations that may affect the determination of the PP populations. Further details of DSMB responsibilities are included in the DSMB Charter.

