12.5.2 Analysis of the Secondary Efficacy Endpoints

12.5.2.1 Change from Baseline in the means of Worst Pain Scores at Day 365 Visit

The change from Baseline (Study VMDN-003-2) in mean worst pain score at the Day 365 visit will be analyzed using the same linear mixed method described in Section 8.4.1 for the ITT population. Missing data will be handled according to the method pre-specified in [Section 12.5.1](#)

12.5.2.2 Proportion of Responders (≥50% reduction in mean ADPS) on Day 365

Responders will be defined as participants with at least 50% reduction from Baseline in the mean ADPS at the Day 365 visit. The percent reduction will be computed as follows:

$$\%Change = \frac{Day\ 365\ mean\ ADPS - Baseline\ mean\ ADPS}{Baseline\ mean\ ADPS} \times 100$$

For each 10 completed datasets imputed using the MI method, a generalized linear mixed-effects model for repeated measures based on a logit link function (hereinafter, the categorical Repeated Measures Model) will be used for comparing the percentage of responders between the two study treatment groups. The model will include treatment, visit, treatment-by-visit interaction, and baseline (Study VMDN-003-2) Average Daily Pain Score as covariates with an unstructured variance-covariance matrix. Then the Proc MIANALYZE procedures will be used to generate the point estimate and the corresponding 95% confidence interval. Study visits from main study will include Baseline and Day 180 and extension study Day 270 and Day 365 will be included.

The SAS code to be used to conduct the analysis is presented below:

```
PROC GLIMMIX DATA=work method=REML;
class usubjid trtp avisitn;
MODEL critvar(event='Y') = trtp base avisitn trtp*avisitn / DIST=binary LINK=LOGIT SOLUTION;
random INTERCEPT / SUBJECT=usubjid type=un;
lsmeans trtp *avisitn / diff cl; RUN;
```

where

USUBJID: subject ID TRTP: treatment

AVISITN: variable representing visits

CHG: change in Average Daily Pain Score from baseline(Study VMDN-003-2)

BASE: (Study VMDN-003-2) Average Daily Pain Score (continuous variable)

CRITVAR: a Y/N variable indicating if the participant had at least a 50% reduction in Average Daily Pain Score from baseline (Study VMDN-003-2) at that visit

Other variance-covariance structures selected from among compound symmetry, Toeplitz, and autoregressive (1) options will be substituted based on the lowest AIC if convergence problems arise.

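### The SAP sets no order, gatekeeping or adjustment for the secondary efficacy comparisons, and does not settle whether there are two or four of them

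*SAP*

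**What the plan says.** **Level.** SAP 12.0 gives one general rule: "All inferential statistical analyses will be performed with a two-sided confidence level of 95% or a two-sided significance level of 0.05 unless otherwise noted". No readable section notes otherwise for the secondary endpoints.

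**Multiplicity.** The one SAP sentence on the subject is in 10.5: "There will be no adjustment for multiple testing due to the DSMB data review". Protocol 10.1.5.1 says the same. Both concern DSMB safety looks, not endpoints or visits.

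**Number of comparisons, endpoint lists.** Protocol 9.3.2 lists worst pain and 50% responders, each from Day 0 "to the 7 days prior to the Day 270 Visit and the 7 days prior to the Day 365 Visit for Engensis compared to Placebo". The SAP 7.0 table agrees. Its worst-pain entry begins "Change in the means of the Worst Pain Scores from the BPI-DPN from the 7 days prior to the Day 0 Visit", and both secondary entries run "to the 7 days prior to the Day 270 Visit and Day 365 Visit for Engensis compared to Placebo". Two endpoints at two visits make four comparisons.

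**Number of comparisons, analysis section.** SAP 12.5.2 names one visit. The worst-pain heading is "12.5.2.1 Change from Baseline in the means of Worst Pain Scores at Day 365 Visit". For the other endpoint, "Responders will be defined as participants with at least 50% reduction from Baseline in the mean ADPS at the Day 365 visit", and the percent-change formula uses the Day 365 mean only. That makes two comparisons.

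**Model output.** Both models include Day 270 as a visit. The responder code requests treatment-by-visit differences ("lsmeans trtp *avisitn / diff cl; RUN"). The primary model's code, reused for worst pain, requests by-visit differences with p-values. Day 270 contrasts will therefore be produced whether or not they are meant as formal tests.

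**The concern.** This is a Phase 3, placebo-controlled extension whose stated purpose is durability of efficacy. Worst pain and response at Days 270 and 365 are natural support for a durability statement.

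With a flat 0.05 for each analysis and no testing rule, nothing in the plan says how a secondary p<0.05 should be read if the primary is not significant, or if only one of several secondaries crosses the line. The chance of at least one false secondary finding grows with the number of comparisons. The plan leaves that number open, so it could be settled after the results are seen.

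**Working it through.** **Inputs**

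- Per-test level: 0.05 two-sided (SAP 12.0).
- Secondary comparisons, k: 4 (Protocol 9.3.2, SAP 7.0) or 2 (SAP 12.5.2.1 and 12.5.2.2).
- Primary: one comparison, ADPS change at Day 365 in the ITT population (SAP 12.5.1).
- Correlations between test statistics: not given in the documents, so assumed.

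The plan states no family-wise figure to reproduce. With k = 1, the formula below returns 0.05, the level in SAP 12.0.

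**Step 1. Independent tests, no true effect.** P(at least one p<0.05) = 1 − 0.95^k.

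- k = 2: 1 − 0.9025 = 9.75%, or 1.95 times 0.05.
- k = 4: 1 − 0.8145 = 18.5%, or 3.7 times 0.05.

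With the primary also independent and not significant, multiply by 0.95. For k = 4 this gives 0.95 × 0.1855 = 17.6%, and for k = 2 it gives 0.95 × 0.0975 = 9.3%.

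**Step 2. One common correlation.** All these scores come from the same diary, and response is a cut of ADPS change, so positive correlation is expected. Simulated multivariate normal z-statistics (2,000,000 draws, cut at 1.96) give:

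| Correlation | Any of 4 | Any of 2 | Any of 4, primary not significant |
|---|---|---|---|
| 0 | 18.5% | 9.75% | 17.6% |
| 0.5 | 15.6% | 9.1% | 13.3% |
| 0.7 | 13.0% | 8.3% | 9.9% |
| 0.8 | 11.4% | 7.8% | 7.7% |

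**Step 3. Correlations that differ by pair.** Assumed ranges:

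- between visits: 0.5 to 0.8
- ADPS with worst pain: 0.7 to 0.9
- ADPS with responder: 0.6 to 0.8
- worst pain with responder: 0.42 to 0.85

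The visit correlation is common to all endpoints, and combinations that do not form a valid correlation matrix are left out. Simulation over these ranges gives:

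| Event, no true effect | Four tests | Two tests |
|---|---|---|
| At least one secondary p<0.05 | about 11% to 16.5% | about 7% to 9% |
| The same, primary not significant | about 8% to 14% | about 4% to 7% |

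The last pair matters. If worst pain with responder is set to the product of the two ADPS correlations (0.42 to 0.72), the four-test range is 12.7% to 16.5%. Raising it to 0.85 brings the low end to about 11%.

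**Step 4. Direction.** These percentages count significance in either direction. Counting only results in Engensis's favour, four tests give 9.6% if independent or 7.8% at a common correlation of 0.5, against 2.5% for one test.

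**Step 5. With a fixed sequence.** If the secondaries are tested in order only after a significant primary, each at 0.05, the family-wise error over primary and secondaries is at most 0.05. With no true effect, the chance of any secondary claim is then about 0.25% if independent (0.05 × 0.05), 0.9% at correlation 0.5 and 2.2% at 0.8.

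**The case against.** The strongest reply has four parts.

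1. **Count.** SAP 12.5.2, the section that specifies the analyses, names Day 365 only, and no sentence there makes Day 270 a formal test. This stands. A reader might infer that four comparisons are each formally tested and that a false secondary finding is therefore about three times as likely as 0.05. The documents do not support that as a fact. It needs the count of four and correlations near 0.5 to 0.6. With two tests the factor is below 2.
2. **Nature of the 0.05.** A reader might infer that a stated error rate is breached. It is not. SAP 12.0 sets a level for each analysis and promises no family-wise level for the secondaries. A rule is missing; no figure is contradicted.
3. **Claims.** The plan does not say that a secondary result will be claimed after a failed primary. It is silent both ways, so the point is the missing rule, not a declared intention.
4. **Setting.** The extension gives no treatment, has no new randomization and no sample-size calculation of its own. Descriptive secondaries would be reasonable here. That is so, but the SAP does not say they are descriptive.

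Redaction is a weak defence. The SAP contents list shows no multiplicity section, the blacked-out block after 12.5.3 falls where that list places the exploratory endpoints, and 12.5.2 itself shows no redaction.

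**Conclusion.** The point holds in this form: the secondary comparisons have no order, no link to the primary and no adjustment, and the SAP does not fix how many there are. Relative to 0.05, the chance of at least one false secondary finding is about 2.2 to 3.3 times for four tests (11/5 to 16.5/5) and about 1.4 to 1.8 times for two (7/5 to 9/5). Independence gives the upper figures of 3.7 and 1.95.

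The size depends on assumed correlations and on how the Day 270 mismatch is resolved. The missing rule depends on neither. The primary analysis is one comparison and keeps its full 0.05; nothing here calls it into question.

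**What to change.** Before unblinding, make two changes in SAP 12.0 and 12.5.2.

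1. State whether Day 270 is a formal secondary comparison, and make 7.0 and 12.5.2 agree.
2. Add a fixed sequence, each step at two-sided 0.05:
   - primary ADPS, Day 365
   - worst pain, Day 365
   - 50% responders, Day 365
   - if Day 270 is formal: worst pain, Day 270, then 50% responders, Day 270

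Stop at the first non-significant step and label all later p-values nominal. The sponsor may choose another order for the secondaries, provided it is fixed before unblinding. If no secondary claims are intended, one sentence labelling all secondary p-values descriptive is enough instead.

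The cost is about one paragraph, with no new data and no loss of alpha for the primary. The downside of the sequence is that a later secondary cannot be claimed once an earlier step fails, however small its p-value.
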